1. SYNOPSIS

Protocol Title: A Phase III, Randomized, Multicenter, Open-Label Study in Adolescent and Adult Participants Comparing the Efficacy and Safety of Gepotidacin to Ceftriaxone Plus Azithromycin in the Treatment of Uncomplicated Urogenital Gonorrhea Caused by *Neisseria gonorrhoeae*

Short Title: Phase III, Comparator-Controlled, Efficacy and Safety Study of Gepotidacin in the Treatment of Uncomplicated Urogenital Gonorrhea; Efficacy of Antibacterial Gepotidacin Evaluated (EAGLE-1)

Rationale:

Gonorrhea is the second most prevalent bacterial sexually transmitted infection globally and remains an important clinical and public health problem throughout the world. A variety of antimicrobial agents have been used over the years for the treatment of gonorrhea; however, effective treatment options for gonorrhea have diminished rapidly because of the emergence and worldwide spread of antimicrobial resistance to many drugs previously used or considered first line. Gepotidacin is a first-in-class, novel triazaacenaphthylene antibacterial that has demonstrated in vitro activity against *Neisseria gonorrhoeae* (NG) with gepotidacin MIC₉₀ values of 0.25 and 1 µg/mL for ciprofloxacin-susceptible and -resistant strains, respectively. In a Phase II study of urogenital gonorrhea caused by NG, microbiological success (bacterial eradication) was demonstrated for 97% and 95% of participants treated orally with single doses of 1500 and 3000 mg gepotidacin, respectively. This Phase III study aims to evaluate oral gepotidacin compared to intramuscular (IM) ceftriaxone plus oral azithromycin, a currently recommended treatment regimen, for the treatment of uncomplicated urogenital infection caused by NG in adolescent and adult participants.

Objectives and Estimands/Endpoints:

Objectives	Endpoints

Primary
 
 To evaluate the efficacy of oral gepotidacin compared to IM ceftriaxone plus oral azithromycin to treat participants with uncomplicated urogenital gonorrhea caused by NG 	
 Culture-confirmed bacterial eradication of NG from the urogenital body site (i.e., microbiological success) at the TOC (Day 4 to 8) Visit

Secondary
 
 To evaluate the efficacy of oral gepotidacin compared to IM ceftriaxone plus oral azithromycin to treat participants with rectal gonorrhea caused by NG To evaluate the efficacy of oral gepotidacin compared to IM ceftriaxone plus oral azithromycin to treat participants with pharyngeal gonorrhea caused by NG To evaluate the safety and tolerability of oral gepotidacin compared to IM ceftriaxone plus oral azithromycin 	
 Culture-confirmed bacterial eradication of NG from the rectal body site (i.e., microbiological success) at the TOC (Day 4 to 8) Visit Culture-confirmed bacterial eradication of NG from the pharyngeal body site (i.e., microbiological success) at the TOC (Day 4 to 8) Visit Treatment-emergent adverse events and serious adverse events and change from baseline results for clinical laboratory tests and vital sign measurements

Note: Exploratory objectives are described in the main protocol text.

Estimands:

The primary clinical question of interest is: What is the treatment effect on the culture-confirmed bacterial eradication of NG from the urogenital body site (i.e., microbiological success) at the TOC (Day 4 to 8) Visit after treatment with oral gepotidacin compared to IM ceftriaxone plus oral azithromycin in participants with uncomplicated urogenital gonorrhea and have confirmed NG isolated from baseline culture of their urogenital specimen, regardless of treatment discontinuation for any reason.

The primary estimand is described by the following attributes:

- Population: Participants with uncomplicated urogenital gonorrhea caused by culture-confirmed NG.
- Treatment condition: Gepotidacin 2×3000 mg versus ceftriaxone 500 mg plus azithromycin 1 g, regardless of adherence.
- Variable: Microbiological success: Participants with culture-confirmed bacterial eradication of NG from the urogenital body site (i.e., urogenital microbiological success) at the TOC (Day 4 to 8) Visit without the participant receiving other systemic antimicrobials before this visit.

- Summary measure: Difference in proportions (microbiological success rate in the gepotidacin treatment group - ceftriaxone plus azithromycin treatment group).
- Intercurrent events:
 - Participants who receive systemic antimicrobials before the TOC Visit will be considered microbiological failures (composite strategy).
 - For study treatment discontinuation, the data will be analyzed as collected (treatment policy strategy).

Components of estimands for all secondary endpoints are provided in Table 3.

The rationale for a treatment policy intercurrent event strategy of study treatment discontinuation is that interest lies in the treatment effect irrespective of whether the full course of treatment was taken or not, this is reflective of how patients may be treated in clinical practice.

The rationale for using a composite strategy for the intercurrent event of antimicrobial use is because usage could affect bacterial culture response; thus, a conservative approach has been adopted and if a participant receives systemic antimicrobials before the TOC Visit, the participant will be assumed to be a microbiological failure. Note: The intercurrent event of antimicrobial use is not applicable for the safety estimands.

Overall Design:

- BTZ116577 is a Phase III, open-label (sponsor-blinded), parallel-group, multicenter, comparator-controlled, noninferiority study in adolescent and adult participants comparing the efficacy and safety of oral gepotidacin to IM ceftriaxone plus oral azithromycin in the treatment of uncomplicated urogenital gonorrhea caused by NG.
- Participants will be stratified by sex and sexual orientation combination and age; and will be randomly assigned to receive either oral gepotidacin or IM ceftriaxone plus oral azithromycin.
- Appropriate safety and microbiological assessments will be conducted at the Baseline (Day 1) Visit and repeated at the TOC (Day 4 to 8) and Follow-up (Day 14 to 21) Visits.
- “Test-of-Cure” microbiological success will be defined by body site (i.e., urogenital and, as appropriate, pharyngeal and/or rectal) as culture-confirmed bacterial eradication of NG observed at the TOC (Day 4 to 8) Visit.

Number of Participants:

Approximately 620 participants will be screened and randomized to achieve approximately 400 participants with culture-confirmed urogenital gonorrhea in the Microbiological Intent-to-Treat (micro-ITT) Population, for an estimated total of 200 participants per treatment group in the micro-ITT Population. Enrollment will continue until the target number of participants in the micro-ITT Population has been reached.

Treatment Groups and Duration:

- Participants will receive 1 of the following treatments:
 - Gepotidacin: 3000 mg administered orally at the study site during the Baseline (Day 1) Visit followed by self-administration of a second oral 3000-mg dose as an outpatient 10 to 12 hours after the first dose; however, for participants who weigh <50 kg or have moderate renal impairment, the second dose should be taken approximately 12 hours after the first dose). (Note: Each dose should be taken after food consumption and with water to assist with tolerability.)
 - Ceftriaxone plus azithromycin: A single IM 500-mg dose of ceftriaxone plus a single oral 1-g dose of azithromycin administered at the study site during the Baseline (Day 1) Visit. (Note: Azithromycin should be taken after food consumption and with water.)
- The duration of study participation is approximately 21 days with 3 planned study visits:
 - Baseline (Day 1) Visit
 - TOC (Day 4 to 8) Visit
 - Follow-up (Day 14 to 21) Visit

Data Monitoring or Other Committee: Yes; an internal GSK Safety Review Team will monitor blinded safety data and an internal Microbiology Review Team will monitor blinded microbiological data instream. No external data monitoring review committees are planned for the study.

2. SCHEDULE OF ACTIVITIES

Table 1 Schedule of Activities

Procedure	Visit ^a	Baseline		TOC ^b	Follow-up ^c	Early Withdrawal
	Study Day	1		4 to 8	14 to 21	NA
	Predose	Postdose	NA	NA	NA	NA
Written informed consent/assent	X					
IRT – Screening module	X					
Inclusion and exclusion criteria	X					
Participant demography	X					
Participant social and sexual history ^d	X					
Medical/surgical history	X					
Diagnosis of presumptive uncomplicated urogenital gonorrhea	X					
Bacteriology samples ^e	X		X	X	X	X
NAAT assay samples ^f	X		X	X	X	X
Physical examination (including height and weight at Baseline only) ^g	X		X			
12-lead electrocardiogram ^h	X					
Vital sign measurements ⁱ	X		X			
Hematology, chemistry, and urinalysis	X		X			
Serology (hepatitis B and C and HIV) ^j	X					
Urine pregnancy test ^k	X ^k		X			X
Drug and alcohol screen	X					
IRT – Randomization module	X					
Administer oral gepotidacin ^l		X ^l				
Administer IM ceftriaxone plus oral azithromycin ^m		X ^m				
Sexual history since last visit ^d			X	X	X	X
Serious adverse events ⁿ	X	X	X	X	X	X
Adverse events ^o		X	X	X	X	X
Concomitant medication review	X	X	X	X	X	X
Schedule TOC and Follow-up Visits	X ^{p,q}		X ^q	X ^p		
Treatment for CT and/or Mgen infection ^r			X	X		X
Genetic sample ^s	X					

CT=*Chlamydia trachomatis*; HIV=human immunodeficiency virus; IM=intramuscular; IRT; interactive response technology; Mgen=*Mycoplasma genitalium*; NA=not applicable; NAAT=nucleic acid amplification test; TOC=Test-of-Cure.

- a. For all study visits, to minimize the amount of time that participants spend at the clinic, eConsent may be utilized and remote collection of study-related data may be obtained as described in the Study Reference Manual. Thus, some visit data may be collected through a combination of telemedicine and on-site visits. Collection of information via telemedicine will be performed only where local regulations permit.
- b. TOC (Day 4 to 8) Visit: Participants will be instructed to return to the study site within 3 to 7 days after study treatment administration. This visit may occur earlier if participants experience an adverse event.
- c. Participants will be instructed to return to the study site from Day 14 to 21 for a Follow-up Visit. The investigator and/or study site staff should make every effort to ensure the participant returns for this visit. If the participant is unable to return to the study site, the visit assessments may be completed via telephone, with the exception of assessments requiring sample collection for laboratory testing.
- d. Refer to the Study Reference Manual for information to collect for social and sexual history.
- e. See Table 2 for collection of bacteriology samples. Also refer to the laboratory manual.
- f. See Table 2 for collection of NAAT assay samples. Also refer to the laboratory manual.
- g. A complete physical examination will be performed at the Baseline Visit and a gonorrhea-focused examination will be performed at the TOC Visit (see Section 9.4.1). Height and weight will only be measured and recorded at the Baseline Visit (before dosing).
- h. See Section 6.2 for electrocardiogram exclusion criterion for participants aged ≥ 12 to < 18 years. For additional details see Section 8.1.2 and Section 9.4.3.
- i. Take measurement of temperature, blood pressure, and pulse rate. See Section 9.4.2.
- j. If serology testing was performed within 3 months prior to the first dose of study treatment and results were **positive**, testing at Baseline **is not required**. If testing was performed within 3 months and any result was **negative**, testing at Baseline **is required**.
- k. For women of childbearing potential, a negative urine pregnancy test is sufficient for eligibility. See Appendix 6 for Baseline urine test sensitivity requirements and associated contraception requirements.
- l. During the Baseline Visit, participants randomly assigned to gepotidacin will receive their first oral dose (3000 mg) at the study site. Participants will self-administer their second dose (3000 mg) as an outpatient 10 to 12 hours after the first dose; however, for participants who weigh < 50 kg or have moderate renal impairment, the second dose should be taken approximately 12 hours after the first dose). See Section 7.1. Each dose should be taken after food consumption and with water to assist with tolerability. Participants will be contacted to confirm that they took their second gepotidacin dose. See Section 7.6.
- m. During the Baseline Visit, participants randomly assigned to ceftriaxone plus azithromycin will receive a single IM dose of ceftriaxone (500 mg) plus a single oral dose of azithromycin (1 g). See Section 7.1. Azithromycin should be taken after food consumption and with water.
- n. Record serious adverse events from the time of consent/assent in order to fulfill international regulatory requirements.
- o. Record adverse events from the time of the first dose of study treatment.
- p. Confirm return day/time for the TOC and Follow-up Visits.
- q. Previsit reminder: Study site staff will contact the participant 24 ± 4 hours before the respectively scheduled Baseline (if applicable), TOC, or Follow-up Visit.
- r. Participants who tested positive for CT and/or Mgen per NAAT results at the Baseline Visit should be treated per local standard of care at or after the TOC Visit or at the Follow-up Visit (if treatment has not already been initiated), as required, after all study procedures at the visit have been completed.
- s. Collect sample only if the participant has a signed consent/assent specific for this purpose. The Baseline Visit is the recommended time to collect the sample; however, it can be collected at any time during the study.

Table 2 Collection of Bacteriology and NAAT Microbiological Specimens

Visit	Baseline	TOC ^a	Follow-up	Early Withdrawal
Study Day	1	4 to 8	14 to 21	NA
Collection Type Anatomical Site ^b – Organism	Pre-dose	NA	NA	NA
Bacteriology sample collection ^b				
Urogenital – NG ^c	X	X		X
Pharyngeal – NG ^d	X	X	X ^e	X
Rectal – NG ^d	X	X		X
NAAT assay sample collection ^f				
Urogenital – NG and CT ^g	X	X ^h		X
Urogenital – Mgen ^g	X		X ⁱ	X
Pharyngeal – NG and CT ^j	X	X	X ^k	X
Rectal – NG and CT ^j	X	X		X

CT=*Chlamydia trachomatis*; Mgen=*Mycoplasma genitalium*; NA=not applicable; NAAT=nucleic acid amplification test; NG=*Neisseria gonorrhoeae*; TOC=Test-of-Cure.

- Any participant that withdraws before TOC should have all bacteriology and NAAT assay collections performed as indicated at the TOC Visit.
- Multiple swab specimens and types may need to be obtained from each anatomical site; refer to the laboratory manual.
- Collect a pretreatment urogenital swab specimen from all participants for Gram stain (males and females), bacterial culture, and in vitro susceptibility testing at Baseline. At TOC, a urogenital swab specimen will be collected for Gram stain, bacterial culture, and in vitro susceptibility testing. Note: **All** urogenital swab specimens will be processed for Gram stain testing following inoculation of the culture plates.
- Pretreatment rectal and pharyngeal swab specimens for bacterial culture and in vitro susceptibility testing will be obtained from participants who are willing to provide such specimens, regardless of known exposure. At TOC, swab specimens will be collected from pharyngeal and/or rectal sites that were collected at Baseline for bacterial culture and in vitro susceptibility testing. Note: **None** of the rectal or pharyngeal swab specimens will be processed for Gram stain testing.
- At Follow-up, pharyngeal swab specimens will be obtained for bacterial culture and in vitro susceptibility testing from participants who had a positive NAAT assay for pharyngeal NG at **both** Baseline and TOC. Results from the NAAT assay will be available to the study sites by the Follow-up Visit.
- See the laboratory manual for local versus central laboratory details and the number and type of specimens to collect.
- Pretreatment baseline urogenital specimens will be obtained from all participants for detection of NG, Mgen, and CT by NAAT. At Baseline, while detection of NG and CT by NAAT may be performed using the same urogenital sample, 2 separate samples must be obtained (1 for the local laboratory and 1 for the central laboratory).
- Urogenital specimens will be obtained from all participants for detection of NG and CT by NAAT at the TOC Visit.
- At Follow-up, a urogenital specimen will be collected for the detection of Mgen only by NAAT from participants who had a positive NAAT assay for Mgen at Baseline. Results from the NAAT assay will be available to the study sites by the Follow-up Visit.
- Pretreatment baseline pharyngeal and rectal specimens for detection of NG and CT by NAAT will be obtained from participants who are willing to provide such specimens, regardless of known exposure. At TOC, a specimen will be collected from pharyngeal and/or rectal sites that were collected at Baseline.
- At Follow-up, a pharyngeal specimen will be collected for detection of NG and CT by NAAT from participants whose NAAT assay had the presence of nucleic acid for NG at **both** Baseline and TOC. NAAT assay results will be available to the study sites by the Follow-up Visit.

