5. STUDY DESIGN

5.1. Overall Design

[figure not shown]
- BTZ116577 is a Phase III, open-label (sponsor-blinded), parallel-group, multicenter, comparator-controlled, noninferiority study in adolescent and adult participants comparing the efficacy and safety of oral gepotidacin to IM ceftriaxone plus oral azithromycin in the treatment of uncomplicated urogenital gonorrhea caused by NG.
- Participants will be stratified by sex and sexual orientation combination (men who have sex with men [MSM], men who have sex with women [MSW], or female) and age (<18 years, ≥18 to 65 years, or >65 years). The MSM category will include MSM and bisexual males (i.e., male participants who have sex with both males and females). Participants will be randomly assigned to receive 1 of the following treatments (see Section 7.1):
 - Gepotidacin: 3000 mg administered orally at the study site during the Baseline (Day 1) Visit followed by self-administration of a second oral 3000-mg dose as an outpatient 10 to 12 hours after the first dose; however, for participants who weigh <50 kg or have moderate renal impairment, the second dose should be taken approximately 12 hours after the first dose. (Note: Each dose should be taken after food consumption and with water to assist with tolerability.)
 - Ceftriaxone plus azithromycin: A single IM 500-mg dose of ceftriaxone plus a single oral 1-g dose of azithromycin administered at the study site during the Baseline (Day 1) Visit. (Note: Azithromycin should be taken after food consumption and with water.)
- Appropriate safety and microbiological assessments will be conducted at the Baseline (Day 1) Visit and repeated at the TOC (Day 4 to 8) and Follow-up (Day 14 to 21) Visits.
- “Test-of-Cure” microbiological success will be defined by body site (i.e., urogenital and, as appropriate, pharyngeal and/or rectal) as culture-confirmed bacterial eradication of NG observed at the TOC (Day 4 to 8) Visit, which is 3 to 7 days posttreatment per Food and Drug Administration (FDA) guidance [DHHS, 2015].
- Participants may return to the study site before the TOC Visit due to AEs.

- Participants who test positive for a CT and/or Mgen infection per baseline NAAT results should be treated per local standard of care at or after the TOC Visit or at the Follow-up Visit (if treatment has not already been initiated), as required, after all study procedures at the visit have been completed (see Section 7.8).

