- **TOC (Day 4 to 8) Visit:** Participants will be instructed to return to the study site 3 to 7 days following study treatment administration at Baseline in order to complete the TOC Visit. Assessments will be performed as shown in Table 1, including the following:
 - The TOC Visit will be preceded by a documented reminder contact from the study site to the participant 24±4 hours before the scheduled appointment time per the method (e.g., text message, telephone call, e-mail) confirmed with the study site staff prior to departing the study site on Day 1.
 - Specimens for microbiological testing will be collected as described in Section 9.1 and Table 2.
 - Participants may return to the study site before the scheduled TOC Visit due to AEs.
 - Participants testing positive for a CT and/or Mgen infection per baseline NAAT results should be treated, as required, per local standard of care at the TOC Visit only after completion of all visit procedures or at any point after the TOC Visit.
 - Participants with culture-confirmed bacterial persistence of urogenital and, as appropriate, pharyngeal and/or rectal NG should receive appropriate alternative therapy per the investigator's choice either on or after the TOC Visit, based on availability of results.
- **Follow-up (Day 14 to 21) Visit:** Participants will be instructed to return to the study site 14 to 21 days following study treatment administration at Baseline in order to complete the Follow-up Visit. Assessments will be performed as shown in Table 1, including the following:
 - The Follow-up Visit will be preceded by a documented reminder contact from the study site to the participant 24±4 hours before the scheduled appointment time per the method (e.g., text message, telephone call, e-mail) confirmed with the study site staff prior to departing the study site on Day 1.
 - The investigator and/or study site staff should make every effort to ensure a participant returns for this visit. If it is determined that the participant is unable to return to the study site, the Follow-up Visit assessments may be completed via telephone, with the exception of assessments requiring sample collection for laboratory testing.
 - Specimens for microbiological testing will be collected as described in Section 9.1 and Table 2.
 - Participants may return to the study site before the scheduled Follow-up Visit due to AEs or if they feel they are not responding to any alternative therapy started after the TOC Visit.

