5.6. Analysis Visits

Due to participants potentially returning outside the protocol scheduled visit window, analysis visit windows will be defined for by-visit summaries and analysis purposes as illustrated in the table below. Data not reported by-visit, including adverse events and concomitant medications, will not employ analysis visits. Analysis visit labels will be assigned to each post-baseline record (including records from unscheduled and early termination visits) based on the corresponding study day (relative to first study treatment or randomization if not treated). For post-baseline records collected outside the analysis visit window, a blank analysis visit label will be assigned. For example, a record collected at study Day 11 will not be utilized in any analyses conducted at the TOC or FU scheduled visit. Descriptive summaries that are shown for “any assessment post baseline” e.g., maximum/minimum/ worst case post baseline, will use all assessments irrespective of whether they fall in an analysis visit window. There are no scheduled FU assessments for Urogenital (except Mgen participants) or rectal body site, but it is possible that any unscheduled assessment or a late TOC fall into this FU window and in that case FU visit will not be presented in summaries but in listings it will be included.

Scheduled Post-baseline Visit	Protocol Window	Target Day	Analysis Visit Window (Days)
Test-of-Cure	4 to 8	6	4 to 10
Follow-up	14 to 21	18	13 to 24

If multiple records exist within the same analysis visit window, then the record occurring closest to the target day will be utilized in all analyses and analysis population determinations. If multiple records are equally close to the target day, then the later record will be utilized. If multiple records occur on the same day and time is not collected, then the record with the larger Study Data Tabulation Model (SDTM) record sequence number will be utilized in all analyses. All protocol scheduled assessments (including unscheduled and early termination visits) will be presented in subject listings. Both the nominal and analysis visit will be presented in listings.

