7.1.1. Endpoint / Variables

The primary efficacy endpoint is culture-confirmed bacterial eradication of NG from the urogenital body site (i.e., microbiological success) at the TOC visit.

- Only those participants who have central laboratory confirmed NG from culture of their baseline bacteriology specimen will be evaluated for microbiological outcome and response. Ceftriaxone susceptibility will be evaluated by applying CLSI MIC breakpoints to results from ceftriaxone agar dilution testing. If an agar dilution value is not available for ceftriaxone, CLSI disk diffusion breakpoints will be applied to results from ceftriaxone disk diffusion testing. The microbiological outcome and response to study treatment will be determined by prespecified programmed algorithm for each participant (see Table 2).
- The microbiological outcome is determined by comparing the baseline culture results to the respective culture results at the TOC visit. The corresponding microbiological response (success or failure) “by participant” is then assigned. The criteria of microbiological participant level outcome and response is shown in Table 2.
- Participant level microbiological success refers to participants who have been deemed a “microbiological success” based on their microbiological response. All other participants are deemed “microbiological failures” for participant level microbiological response.

Table 2 Microbiological Outcome and Response at the Test-of-Cure Visit

Defining Criteria	Microbiological Outcome	Microbiological Response
Culture-confirmed elimination of baseline pathogen (NG) from a bacteriology sample taken at the TOC visit without the participant receiving other systemic antimicrobials before this visit	Bacterial eradication	Microbiological success
Culture-confirmed persistence of baseline NG pathogen from a bacteriology sample taken at the TOC visit without the participant receiving other systemic antimicrobials before this visit	Bacterial persistence	Microbiological failure
1) A determination of the TOC NG pathogen microbiological outcome cannot be made (e.g., no bacteriological sample taken for culture, sample lost, visit did not occur etc.) 2) The participant received other systemic antimicrobials before the TOC visit	Unable to determine	Microbiological failure

1. TOC=Test-of-Cure.
2. Note: A bacteriological specimen refers to a urogenital specimen obtained for bacteriological culture.

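### The schedule footnote lets the TOC visit be moved before Day 4 for an adverse event, but the SAP cannot use a culture taken then, so an eradicated infection can be scored as a failure

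*Protocol*

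**What the plan says.** **Visit schedule.** Footnote b of protocol Table 1 places TOC at Day 4 to 8 ("Participants will be instructed to return to the study site within 3 to 7 days after study treatment administration") and then adds: "This visit may occur earlier if participants experience an adverse event". It sets no earliest day and does not ask for a repeat culture. SAP Table 5 (Appendix 1) carries the same footnote.

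**Body text.** Protocol Section 5.1 says "Participants may return to the study site before the TOC Visit due to AEs". Section 9, under the TOC visit, says "Participants may return to the study site before the scheduled TOC Visit due to AEs". Both describe an additional attendance and leave the TOC visit where it was.

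**Analysis windows.** SAP Section 5.6 sets the TOC window at Day 4 to 10 and allocates records by study day, not by visit name: "Analysis visit labels will be assigned to each post-baseline record (including records from unscheduled and early termination visits) based on the corresponding study day". Outside the windows, "For post-baseline records collected outside the analysis visit window, a blank analysis visit label will be assigned". The SAP's own example is a late record: "a record collected at study Day 11 will not be utilized in any analyses conducted at the TOC or FU scheduled visit".

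**Scoring.** In SAP Section 7.1.1, Table 2, one route to the unable-to-determine category is "A determination of the TOC NG pathogen microbiological outcome cannot be made". That category is a microbiological failure.

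**Later cultures.** Protocol Table 2 and Section 9.1.1 schedule no urogenital or rectal culture at Follow-up. Only pharyngeal specimens are cultured then, and only for selected participants.

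**The concern.** The footnote and the body text give a site two different instructions for a participant who comes back on Day 2 or 3 with an adverse event. Under Sections 5.1 and 9 the site deals with the event and still expects the participant for TOC. Under the footnote it may carry out the TOC procedures there and then. Protocol Section 9 says that adherence to Table 1 is required, so following the footnote would not be a misreading.

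If the footnote is followed and nothing is cultured on Day 4 to 10, the primary endpoint is decided by visit timing and not by persistence of infection. The trigger is an adverse event after open-label treatment, so the loss need not be equal between arms. Unequal losses shift the estimated difference in success rates, which is the quantity tested against the -10% margin.

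**Working it through.** **Step 1: follow one participant through the rules.** TOC is held on Day 3 for an adverse event, the urogenital culture is negative, and no culture is taken on Day 4 to 10.

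| Rule | Result |
|---|---|
| Schedule footnote b | TOC on Day 3 is permitted |
| Protocol Table 2, Section 9.1.1 | No urogenital or rectal culture at Follow-up |
| SAP 5.6, window Day 4 to 10 | Day 3 culture has a blank visit label |
| SAP 7.1.1, Table 2 | Unable to determine, hence failure |
| SAP 7.1.6.2, multiple imputation | Covers COVID-19 misses and samples without a result; this sample has a result, so it stays a failure |
| SAP 4, ME population | Needs a TOC specimen with a culture result, so the participant is dropped |

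Laboratory tests and vital signs have one scheduled post-baseline time, TOC. Day 3 values therefore leave the by-visit summaries, but SAP 5.6 keeps them in worst-case summaries and in listings.

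**Step 2: reproduce the plan's power.** Protocol Section 10.2.1 gives 200 per arm, 90% success in both arms, a -10% margin, one-sided 0.025, and about 91% power. With the unpooled normal approximation,

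power = Φ((0.10 + pG − pC)/SE − 1.96), SE = √(pG(1−pG)/200 + pC(1−pC)/200).

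At pG = pC = 0.90, SE = 0.0300 and power = Φ(3.333 − 1.96) = 91.5%. This agrees with the plan. Exact enumeration of the unstratified Miettinen-Nurminen test gives 90.0%.

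**Step 3: add the loss.** Let s be success before the loss, and let a and b be the fractions with an unusable early TOC on gepotidacin and comparator. Then pG = s(1−a) and pC = s(1−b). The documents give no values for a and b; those below are assumptions.

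Worked example, s = 0.90, a = 1% (2 of 200), b = 0: pG = 0.891, difference −0.9 points, SE = 0.03059, power = Φ(0.091/0.03059 − 1.96) = 84.5% (Miettinen-Nurminen exact 82.6%).

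| a v b | s = 90% | s = 93% | s = 95% |
|---|---|---|---|
| 0 v 0 | 91.5% | 97.5% | 99.6% |
| 1% v 0 | 84.5% | 93.2% | 97.8% |
| 2% v 0.5% | 78.6% | 88.2% | 94.5% |
| 3% v 1% | 72.0% | 81.8% | 89.2% |

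Equal losses matter little: at s = 90% and 1% in both arms, power is 89.4%.

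The value of s is uncertain. Section 10.2.1 calls 90% conservative and states directly afterwards that non-return for TOC counts as failure, so 90% may already allow for some missing TOC results. The 93% and 95% columns are assumptions that show the sensitivity to this.

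**Step 4: reverse the imbalance.** Suppose the true rates are 80% on gepotidacin and 90% on comparator, exactly at the margin, and early TOC occurs only on the comparator. At 1%, pC = 0.891 and SE = 0.03586, so the chance of declaring noninferiority is Φ((0.10 − 0.091)/0.03586 − 1.96) = 4.4%, against 2.5% with no loss. At 2% it is 7.2%. The exact Miettinen-Nurminen figures are 2.4%, 4.3% and 7.0% for 0, 1% and 2%.

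**The case against.** **The footnote may mean less than it says.** It opens by naming TOC as Day 4 to 8, the table column says the same, and the visit is booked before the participant leaves on Day 1, with a reminder a day beforehand. The sentence can be read as earlier than the booked day but still inside the window. That reading is possible, but the text sets no lower limit and the SAP repeats it unchanged.

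**Failure is not automatic.** A reader might infer that every participant seen before Day 4 becomes a failure. The documents do not support that. SAP 5.6 labels unscheduled records by study day, so any culture on Day 4 to 10 makes the participant evaluable, provided no other systemic antimicrobial came first. The loss needs all three: TOC held before Day 4, the site treating it as complete, and no later culture in the window.

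**The direction is unknown.** A reader might also infer that gepotidacin is the arm at risk, because protocol Section 3.3.1 reports gastrointestinal events as common with it. The same section lists gastrointestinal effects for ceftriaxone and azithromycin, and Section 3.3.2 expects that gepotidacin may be better tolerated. Nothing links such events to site visits before Day 4.

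**The SAP has partial safeguards.** Multiple imputation and the tipping-point analysis may be repeated for all missing TOC responses if missingness is high (Section 7.1.6.2), and Table 2.341 summarises missing data behind unable-to-determine outcomes. These would help, but the repeats are optional and neither changes the primary analysis.

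**Conclusion.** The conflict between the footnote and Protocol Sections 5.1 and 9 is in the text. Followed as written, the footnote can lead the SAP to score an eradicated infection as a failure when no culture follows on Day 4 to 10. An imbalance between arms would bias the noninferiority comparison in whichever direction the imbalance runs.

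The size cannot be stated from the documents. The power and error figures show sensitivity to assumed rates; they do not predict what will happen. At 1% v 0% the loss of power is 7.0 points from a 90% base (91.5% to 84.5%) and 1.8 points from a 95% base (99.6% to 97.8%). The plan's sample size and its stated power are not in error. The effect on safety reporting is limited to by-visit summaries.

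**What to change.** Reconcile footnote b in protocol Table 1 and SAP Table 5 with Protocol Sections 5.1 and 9. It should say that a visit for an adverse event before Day 4 is unscheduled and does not replace TOC, and that all TOC specimens and assessments are still obtained on Day 4 to 8. Add to the SAP a count by arm of participants whose only post-baseline culture was before Day 4, so that any loss already incurred is visible.

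The cost is one footnote in two documents, a letter to sites and one line in an existing summary. The downside is that a participant seen early still has to attend the TOC visit already scheduled.
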